#### 1028   **8.4 Interim Analysis**

1029  
1030   An analysis of primary outcome data, secondary outcome data, and safety data will be provided  
1031   to the DSMC twice each year. A formal statistical plan for interim monitoring of primary  
1032   outcome data will be developed in conjunction with the DSMC.

#### 1033   **8.5 Observation Phase Analysis**

1034  
1035   The primary analysis of observation phase data will consist of estimation of the proportion (and  
1036   95% confidence interval) of patients with recurrence of amblyopia (as defined in section 5.1.4)  
1037   during the observation phase using the Kaplan-Meier method. Additionally, a separate estimate  
1038   and 95% confidence interval for each treatment group also will be obtained.

#### 1039   **8.6 Analysis of active VT phase for non-responding controls**

1040  
1041   The primary analysis of data from this phase will consist of estimation of the proportion and 95%  
1042   confidence interval of patients with treatment success using the exact binomial method. As for  
1043   the primary outcome analysis of the RCT, dropouts during the course of active treatment will be  
1044   considered as treatment failures.

#### 1045   **8.7 Secondary Outcome Analyses**

##### 1046   **8.7.1 Mean improvement in visual acuity**

1047   A secondary analysis consisting of a treatment group comparison of logMAR visual acuity  
1048   scores in the amblyopic eye obtained at the 17-week masked exam, adjusted for baseline visual  
1049   acuity score, will be performed using analysis of covariance (ANCOVA).

##### 1050   **8.7.2 Determination of rate of visual acuity improvement**

1051   Determination of the rate of visual acuity improvement in study patients will be based on all  
1052   visual acuity measurements from the weekly visits, including the baseline and 17-week masked  
1053   exam. Using all available visual acuity measurements, a linear slope of visual acuity over time  
1054   will be computed for each patient and compared between treatment groups using linear mixed  
1055   models methodology. If, based on inspection of individual plots of visual acuity over time and  
1056   average visual acuity over time by treatment group, it appears that the time course of visual  
1057   acuity improvement is not linear, 2 linear slopes of visual acuity over time will be computed for  
1058   each patient. The first slope will be based on visual acuity measurements from baseline through  
1059   week 8, and the second will be based on visual acuity measurements from week 9 through week 17.  
1060   Again, these 2 slopes will be compared between treatment groups using linear mixed models  
1061   methodology. The latter analysis will allow for the possibility that overall visual acuity at 17  
1062   weeks does not differ between the 2 treatment groups, but that one treatment achieves endpoint  
1063   visual acuity sooner than the other.

1064 **8.7.3 Stereoacuity**

1065 Distribution of stereoacuity at the 17-week outcome exam and change in number of categories of  
1066 stereoacuity from baseline to the 17-week masked exam will be compared between treatment  
1067 groups using the exact Wilcoxon rank sum test.

1068 **8.8 Feasibility Phase Analysis**

1069  
1070 The feasibility phase is not powered to be able to detect a difference between treatments in  
1071 effectiveness. Active vision therapy would need to have greater than 80% effectiveness with  
1072 respect to the primary visual acuity endpoint for a treatment difference to have a reasonable  
1073 chance of being detectable with a sample size of 45, a highly unlikely possibility. Hence, no  
1074 statistical testing will be conducted. Rather, the primary goal of data analysis will be descriptive  
1075 in nature, and intended to aid in the evaluation of study feasibility and adherence with treatment  
1076 protocol. This will include:

- 1077
- 1078 • Estimation of recruitment rate (overall and by center);
  - 1079 • Estimation of recruitment rate by prior treatment status;
  - 1080 • Enumeration and review of cases, if any, of ineligible patients enrolled;
  - 1081 • Estimation of the percentage of patients missing the treatment visit for each treatment  
1082 visit (overall, and by treatment);
  - 1083 • Distribution of number of treatment visits missed per patient (overall, by treatment group,  
1084 and by site)
  - 1085 • Estimation of mean and range for number of non-office visit days the home computer  
1086 therapy was used (by treatment group);
  - 1087 • Summary of patient progress through treatment protocol (number and percent of patients  
1088 in each phase by week of treatment and treatment assignment);
  - 1089 • Identification and review of patients making insufficient or very rapid progress with  
1090 treatment (patients appearing as outliers in the above table);
  - 1091 • Enumeration and review of all cases, if any, with adverse events (diplopia, reverse  
1092 amblyopia, development of a new ocular deviation);
  - 1093 • Estimation of retention and dropout rates of enrolled patients at 17 weeks (overall and by  
1094 center);
  - 1095 • Estimation of percentage of patients with valid outcome data for each outcome at 17  
1096 weeks (overall and by center);
  - 1097 • Estimation of the percentage of patients in each treatment group who correctly and  
1098 incorrectly identify their treatment group assignment;
  - 1099 • Estimation of the percentage of patients in the control group not classified as treatment  
1100 responders who elect to undergo a course of active therapy.

1101  
1102 Patients will be classified into 3 groups according to prior treatment status for the purpose of  
1103 estimating recruitment rate within each of the groups. These 3 groups are:

- 1104 • Patients who were not treated for amblyopia within 6 months prior to enrollment;
  - 1105 • Patients who were treated within the past 6 months who initially had severe amblyopia  
1106 and were enrolled in the study after improvement to moderate amblyopia; and
  - 1107 • All other patients who were treated within the past 6 months.
- 1108

1109 The purpose of this stratification is to determine which, if any, of these groups has sufficient  
1110 numbers of patients that they could be targeted for a full-scale trial of vision therapy.

1111

1112 Outcome data consist of data from the testing procedures at the 17-week examination as  
1113 specified in section 4.2.2., and visual acuity data collected at the weekly treatment visits. For the  
1114 purposes of the feasibility assessment, to be considered valid, outcome data must be collected  
1115 according to study protocol-specified procedures and within the designated time window for the  
1116 visit.

1117  
1118 Guidelines for judging successful completion of the feasibility phase with respect to the above  
1119 criteria are specified in a separate document (Sample Size Estimation and Statistical Analysis  
1120 Plan).

1121  
1122

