## 457   **2.4 Examination Procedures**

### 458   **2.4.1 Historical Information**

459   Historical information to be collected will include: date of birth, gender, race, ethnicity, prior  
460   amblyopia therapy (e.g., glasses, patching, pharmacologic, filters, vision therapy), refractive  
461   correction, and history of allergy/intolerance to bandage adhesive.

462 **2.4.2 Clinical Testing for Enrollment**

- 463 1. Visual acuity in each eye (right eye first) is measured by the ATS single-surround eETDRS  
464 testing protocol on the Electronic Visual Acuity Tester. The protocol for conducting the  
465 visual acuity testing is described in the ATS Testing Procedures Manual. Aspects of the  
466 testing protocol that are specific to this study are indicated below:
- 467 • Testing must be done without cycloplegia (with spectacles, if worn) no more than 7 days  
468 prior to randomization.
  - 469 • Because the patient needs to be wearing spectacles that provide best visual acuity to be  
470 enrolled, trial frames/phoropter with a different correction cannot be used to measure  
471 acuity at enrollment.
  - 472 • If the patient has difficulty with the acuity testing, often he or she will perform better  
473 when the testing is repeated. At the investigator's discretion, acuity can be retested on  
474 the same or a subsequent day to assess eligibility.
- 475 2. Ocular motility examination
- 476 • Measurement of predominant alignment by Simultaneous Prism and Cover Test (SPCT)  
477 in primary position at distance and near.
  - 478 • Testing must be done without cycloplegia (with spectacles if worn) no more than 7 days  
479 prior to randomization
- 480 3. Ocular examination as per investigator's clinical routine to rule out a cause for reduced visual  
481 acuity other than amblyopia
- 482 ➤ if performed within prior 6 months, does not need to be repeated at time of  
483 enrollment.
- 484 4. Binocularity testing (without cycloplegia): Titmus Fly and Randot Preschool Stereoacuity  
485 test
- 486 5. Cycloplegic refraction using cyclopentolate 1% as per investigator's usual routine
- 487 ➤ if performed within prior 6 months, do not need to repeat at time of enrollment

488 **2.5 Randomization of Eligible Patients**

489  
490 Assuming that visual acuity in the amblyopic eye on the better of the initial or repeat tests is  
491 20/40 to 20/100, inclusive, and acuity in the sound eye is 20/25 or better, the patient will be  

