**529 3.1.1 Measurement of Visual Acuity**

530 Prior to each in-office therapy session the vision therapist (or other ATS certified visual acuity  
531 tester) will measure the visual acuity of each eye using the eETDRS protocol (*the protocol for*  
532 *conducting the visual acuity testing is described in the ATS Testing Procedures Manual*). The  
533 person completing the visual acuity measurement for in-office therapy sessions will not be  
534 required to be masked to the patient's treatment assignment.

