## 644 **3.3 Home Calendar Logs**

645

646 Parents will record the amount of time the patient wore the patch at home each day.  
647  
648 The calendars will be brought to the weekly office visits and a summary of the data will be  
649 entered onto the study website, along with other data collected at therapy visits.  
650  
651 At each visit, the logs will be reviewed by the therapist and an assessment of patching  
652 compliance recorded on the Follow-up Examination Form.  
653

655 **4.1 Follow-up Schedule**

656

657 All patients will have the following study visits:

- 658 • Weekly office visits  $\pm$  4 days for 16 weeks for administration of in-office vision therapy
- 659 • 17-week masked outcome visit  $\pm$  1 week

660 **4.2 Testing Procedures**661 **4.2.1 Weekly In-Office Vision Therapy Visits**662 The following activities/testing will be performed at the weekly office visits in the specified  
663 order:

- 664 • Binocular diplopia query
  - 665 ○ If a patient reports the onset of constant diplopia, treatment will be discontinued. If
  - 666 diplopia has resolved at the next week's office visit, therapy will be reinstated;
  - 667 however, anti-suppression therapy will not be performed for those assigned to
  - 668 Active vision therapy
- 669 • Measurement of visual acuity in each eye by the eETDRS testing protocol on the  
670 Electronic Visual Acuity Tester
  - 671 ○ The right eye is tested first, then the left eye
  - 672 ○ Testing is performed without cycloplegia with spectacles (if worn)
- 673 • In-Office Vision Therapy
  - 674 ○ Active or Control vision therapy based on randomization
- 675 • Completion of the therapy progress checklist

676

677 All patients will continue to have weekly in-office treatment sessions even if the visual acuity  
678 reaches 20/20 during the study.

679

680 All procedures at weekly vision therapy visits are permitted to be performed by a person who is  
681 unmasked to the patient's treatment assignment.682 **4.2.2 Scheduling of Weekly In-Office Vision Therapy Visits**

683 Ideally, treatment visits should be exactly 7 days apart; however, this will not always be possible.  
684 As such, we have established acceptable visit windows for the time between each in-office vision  
685 therapy visit. The acceptable window for each appointment is  $\pm$  4 days from the original  
686 targeted date (as calculated from the initial therapy session). Furthermore, no more than two  

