687 appointments can be scheduled within a 7 day period and successive appointments must be more  
688 than 2 days apart.

689

690 Coordinators and Vision Therapists should consider creating a standing appointment time for  
691 each patient during the study. Care should be given to not schedule study patients back to back  
692 if possible to help minimize potential interaction between patients in different treatment arms.

693 **4.2.3 17-Week Masked Examination**

694 The following procedures will be performed at the 17-week Masked Outcome Examination. The  
695 visual acuity and stereoacuity tests need to be performed by a masked examiner. The order of  
696 procedures will be:

- 697 1. Binocular diplopia query

- 698 2. Measurement of visual acuity in each eye by the eETDRS testing protocol on the  
699 Electronic Visual Acuity Tester. (Must be performed by a masked examiner. The right  
700 eye is tested first.)  
701 3. Titmus Fly and Randot Preschool Stereoacuity Test (Must be performed by a masked  
702 examiner.)  
703 4. Ocular alignment by SPCT  
704 5. Ask the patient and the parent/guardian if they believe they were receiving active vision  
705 therapy or control therapy  
706 • This must be the last item completed.

707 **4.2.4 Unmasking of treatment assignment**

708 At the completion of the 17-week visit, the patient and parent will be told their treatment group  
709 assignment. Patients in the control group will be offered the opportunity to complete a course of  
710 active vision therapy that will be paid for by the study. To be paid by the study the  
711 parents/patient must decide to enroll in the vision therapy within 10 days after the completion of  
712 the 17-week masked examination.

713  
714

715

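### The two-slope fallback in Protocol section 8.7.2 joins allocation-blind end points to weekly acuity that may be measured unmasked, so a scoring difference between arms could imitate the faster-improvement pattern it looks for

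*Protocol*

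**What the plan says.** **Data used.** Section 8.7.2 of the Protocol takes all "visual acuity measurements from the weekly visits, including the baseline and 17-week masked" exam as one series. A single linear slope per patient is compared between arms in a linear mixed model. If plots of individual acuity and of mean acuity by arm look non-linear, two slopes are fitted instead, split between weeks 8 and 9. The stated reason is to allow for the case where acuity at 17 "weeks does not differ between the 2 treatment groups, but that one treatment achieves endpoint" acuity earlier than the other.

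**Who measures.** The assessor rules differ along that series:

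- Baseline, section 2.4.2: "Testing must be done without cycloplegia (with spectacles, if worn) no more than 7 days" before randomization, so the tester cannot know the arm.
- Weekly visits, section 3.1.1: "Prior to each in-office therapy session the vision therapist (or other ATS certified visual acuity" tester) measures each eye, and the "person completing the visual acuity measurement for in-office therapy sessions will not be" required to be masked. Section 4.2.1 repeats this: "All procedures at weekly vision therapy visits are permitted to be performed by a person who is" unmasked.
- Week 17, section 4.2.3: the "visual acuity and stereoacuity tests need to be performed by a masked examiner".

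Section 8.7.2 gives no check or caveat for the change of assessor.

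**The concern.** A difference between arms in how unmasked testers score, for example through more prompting in one arm, would act at the weekly visits only. It would add a step up after the blind baseline and a step down at the masked exam, and leave week-17 acuity equal. Fitted as two slopes, that looks like faster early gain, a flatter later course and the same endpoint.

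The masked week-17 result cannot expose this, because an equal endpoint is part of the claim. The step could also make the mean plots look non-linear and so help to trigger the two-slope analysis. At stake is a statement that one therapy works sooner when only the tester's knowledge of the arm differed.

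**Working it through.** **Inputs.** From the Protocol: baseline, 16 weekly visits and week 17; slope windows 0 to 8 and 9 to 17; 222 patients, so 222/2 = 111 per arm (section 8.1). That total is reproduced by a one-sided 5% test of 30% against 50% with continuity correction (111 per arm; exact Fisher power 90.0%). The Protocol gives no figure for the rate outcome. Assumed: a constant between-arm bias of d letters at unmasked visits, no true difference, single-test SD 3 to 4 letters, between-patient slope SD 0.3 to 0.6 letters/week.

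**Two slopes, weekly tests at weeks 1 to 16.** The bias is 0 at weeks 0 and 17 and d in between.

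- Early: Σ(t-4)y = 4d and Σ(t-4)² = 60, so the slope shifts by 4d/60 = +0.067d letters/week, or 8 × 0.067d = 0.53d over 8 weeks.
- Late: the mirror image, -0.067d.
- A joined two-slope model with its knot at 8.5 gives the same two values.

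**Two slopes, weekly tests at weeks 0 to 15.** Section 3.1.7 allows the first session on the day of randomization.

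- Early: 3.6d/74.4 = +0.048d.
- Late: -4.375d/49.875 = -0.088d.

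**Single slope, weeks 0 to 17.**

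- Constant bias: the two unbiased points lie symmetrically about 8.5, so the shift is exactly 0 (-0.004d with tests at weeks 0 to 15).
- Bias growing linearly to d at week 16: Σ(t-8.5)y = 21.25d and Σ(t-8.5)² = 484.5, so the shift is 0.044d letters/week.

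**False-positive rate of the early slope, if the two-slope analysis is run.** The standard error of the arm difference is √[(s²/60 + s_b²) × 2/111].

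| s | s_b | SE | d = 1 | d = 2 |
|---|---|---|---|---|
| 3 | 0.3 | 0.066 | 17% | 53% |
| 3 | 0.6 | 0.096 | 11% | 29% |
| 4 | 0.3 | 0.080 | 13% | 38% |
| 4 | 0.6 | 0.106 | 10% | 24% |

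The nominal rate is 5%, two-sided. With SDs of 3 to 5 and 0.1 to 0.5 the ranges are 9 to 24% (d = 1) and 23 to 70% (d = 2). Two letters is under half a line, since section 1.3 equates 15 letters with 3 lines.

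**Can a model term remove the bias?** Consider an arm-by-unmasked-visit term (0 at baseline, 1 at weeks 1 to 16, 0 at week 17). Test it with no assessor bias and a true faster effect: a 10-letter gain in both arms, exponential with time constants of 3 and 5 weeks, scaled to equal week-17 acuity (all assumed).

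- The term reports 0.67 letters of bias that does not exist.
- The early-slope difference falls from 0.085 to 0.040 (separate slopes) and from 0.023 to -0.022 (joined).
- Without the scaling: 0.70 letters, 0.115 to 0.068, and 0.050 to 0.004.

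**Can the last step separate the two cases?** The between-arm difference in the change from week 16 to week 17 is about -d under a constant bias and about -0.06 letters under that true effect. Its standard error is √(2s² × 2/111) = 0.57 for s = 3 and 0.76 for s = 4, so the 95% interval is about ±1.1 to ±1.5 letters.

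**The case against.** A reader might infer that the whole rate-of-improvement outcome is compromised, or that the rates above are its error rates. The Protocol does not support either. The analysis planned first is a single slope, which a constant bias leaves unchanged; it is shifted only under the further assumption of a growing bias. The rates apply only if the two-slope fallback is run.

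Nor do the documents show that a bias exists. It must differ between arms, since an equal bias cancels. Acuity follows the eETDRS protocol on an electronic tester, a tester other than the therapist must be certified, and patients and parents are masked until the week-17 visit is complete. Unmasked weekly testing is permitted openly, not required, so there is no contradiction. Chapter 8 describes itself as a framework that a separate analysis plan will supersede, and that plan may deal with the point.

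All of this stands and limits the finding. What remains is that the Protocol itself fixes who may test, which values are pooled and what conclusion is sought. It requires masking for the same test at week 17, and a later analysis plan cannot change who measured the weekly values.

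It is also tempting to require that the slope difference survive an arm-by-unmasked-visit term. That goes too far: the term has nearly the shape of a genuine faster effect and could suppress one.

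**Conclusion.** The point holds for the two-slope fallback in section 8.7.2 only. A constant between-arm scoring difference of d letters at weekly visits shifts the early and late slopes by about +0.067d and -0.067d letters per week (+0.048d and -0.088d with visits at weeks 0 to 15), with equal week-17 acuity. Under the assumed SDs, the 5% false-positive rate of the early slope becomes about 10 to 17% at one letter and 24 to 53% at two. The existence and size of d, both SDs and the visit timing are assumptions.

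The primary outcome, the ANCOVA and stereoacuity are not touched. This is a modest weakness in one conditional secondary analysis, worth correcting because the remedy needs no new data.

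**What to change.** In section 8.7.2:

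1. Prespecify reporting the change from the last unmasked weekly acuity to the masked week-17 acuity, by arm, with the between-arm difference and its confidence interval.
2. State that a faster-improvement claim from the two-slope analysis will be presented as resting on unmasked measurements. It will not be concluded if that step differs between arms in the direction that would create the pattern. Write down in advance what counts as differing.
3. Show the arm-by-unmasked-visit term, if at all, as a sensitivity analysis and not as a condition for the conclusion.

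**Cost.** One extra descriptive analysis and a more cautious claim. Precision is limited: with a standard error of 0.57 to 0.76 letters, a 95% interval would exclude zero in roughly 75 to 94% of trials for a two-letter bias (2/0.76 = 2.63 and 2/0.57 = 3.51, less 1.96), but only about 26 to 42% for one letter (1/0.76 = 1.32 and 1/0.57 = 1.76). A step close to zero therefore does not clear the weekly data, and the caveat in item 2 is needed whatever the step shows.

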### 260 Primary Analysis

261 The primary outcome measure is the proportion of patients with visual acuity of 20/25 or better

262 in the amblyopic eye at the 17-week masked exam. These patients will be considered treatment

263 responders. The primary analysis will consist of a comparison between the 2 treatment groups of

264 the proportion of treatment responders with adjustment for baseline visual acuity.

265

266 Secondary outcomes are stereoacuity at the 17-week masked exam, mean improvement in visual

267 acuity at the 17-week masked exam, and rate of improvement of visual acuity.

268

269 Sound eye visual acuity will be reported for each treatment group at the 17-week masked exam

270 as mean change from baseline, distribution of number of lines of change from baseline, and

271 number and proportion of patients losing 2 or more lines from baseline.

272

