411                   first of two consecutive measurements: 1) in current glasses, 2) in trial frames  
412                   with full correction of hypermetropia with cycloplegia, or 3) by having the  
413                   patient return in new glasses for the first measurement. The second acuity  
414                   measure does not have to be made through the same prescription as the first, if  
415                   the second measure is made through a more accurate prescription. *Note:*  
416                   *because this determination is a pre-study procedure, the method of measuring*  
417                   *visual acuity is not mandated, although eETDRS testing is preferred if done as*  
418                   *part of usual care.*

- 419                   ▪ Prior contact lens wear is permitted, but patients must be willing to switch to  
420                   spectacles for the duration of the study. Stability of visual acuity in spectacles  
421                   according to above criteria must be documented prior to enrollment.  
422                   ▪ Prior bifocal wear is permitted but patient must switch to and show stability  
423                   with single vision glasses before being enrolled in the study. There can be no  
424                   constant strabismus at near without the bifocals.
- 425   6. Near stereoacuity of 800 seconds of arc or better on the Randot Preschool Stereoacuity test
- 426   7. No previous home-based, office-based or computerized vision therapy or orthoptics
- 427   8. Previous or current amblyopia treatment with spectacles, contact lenses, patching, or  
428   atropine is permitted. At the time of enrollment the patient must be:
- 429       • currently patching for 2 hours per day, *or*
- 430       • ready to be switched to 2 hours per day of patching from another patching dose or  
431       from atropine, *or*
- 432       • not currently on treatment (other than spectacles or contact lenses) and ready to initiate  
433       patching for 2 hours per day.
- 434   The decision whether the patient is a suitable candidate to be switched to 2 hours per day of  
435   patching is at investigator discretion. Atropine treatment must be discontinued at least 2  
436   weeks prior to enrollment. Patients taking atropine may be switched to patching when  
437   atropine is discontinued and enrolled 2 weeks later, if the investigator does not wish to stop  

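### Section 8.7.3 compares stereoacuity by two unadjusted rank tests and names neither as the main one; one baseline-adjusted rank test would be somewhat more powerful and clearer

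*Protocol*

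**What the plan says.** - **Status of the outcome.** Section 1.3 (Primary Analysis) lists stereoacuity first: "Secondary outcomes are stereoacuity at the 17-week masked exam, mean improvement in visual" acuity, and the rate of improvement.
- **Analysis.** Section 8.7.3 sets two comparisons: "Distribution of stereoacuity at the 17-week outcome exam and change in number of categories of" stereoacuity from baseline. Both are made between "groups using the exact Wilcoxon rank sum test". No covariate or stratification is given, and neither comparison is ranked above the other.
- **Baseline data.** Section 2.3, criterion 6, requires "Near stereoacuity of 800 seconds of arc or better on the Randot Preschool Stereoacuity test". Section 2.4.2 lists the enrollment test: "Binocularity testing (without cycloplegia): Titmus Fly and Randot Preschool Stereoacuity" test. Section 4.2.3 repeats both tests at 17 weeks with a masked examiner: "Titmus Fly and Randot Preschool Stereoacuity Test (Must be performed by a masked" examiner.
- **Acuity, for contrast.** Section 8.7.1 compares logMAR "scores in the amblyopic eye obtained at the 17-week masked exam, adjusted for baseline visual" acuity, by ANCOVA. The primary logistic regression in section 8.2 is also adjusted for baseline acuity, and section 8.1 expects that adjustment to raise power.
- **Status of the chapter.** The opening of Chapter 8 calls it a framework that the final analysis plan will supersede.

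**The concern.** The final-value test ignores baseline. The change test uses it, but subtracts it with a weight fixed at one. That adds noise when baseline and final values are only moderately correlated, and a patient already in the best category has no room to improve. An adjusted comparison lets the data set the weight. The sponsor cannot know in advance which planned test will be the stronger, because that depends on a correlation the protocol does not give.

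Two matters are at stake: some chance of detecting a real stereoacuity effect, and a clear reading if the two tests disagree. Section 1.2 gives binocularity, alongside acuity, as a reason for adding vision therapy, so this secondary outcome is of interest.

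**Working it through.** **The plan's own figure.** The protocol states no power or sample size for stereoacuity. Its only relevant figure is the total of 222 for the primary outcome (30% v 50%, one-sided 5%, 90% power). Without continuity correction, n = (1.645·√(2·0.4·0.6) + 1.282·√(0.3·0.7 + 0.5·0.5))² / 0.2² ≈ 100.9, or 101 per arm. With the correction, n = (100.9/4)·(1 + √(1 + 4/(100.9·0.2)))² ≈ 110.7, or 111 per arm and 222 in total. Exact one-sided Fisher power at 111 per arm is 90.0%. The figure reproduces, and 111 per arm is used below.

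**Relative variance.** Let ρ be the baseline-to-final correlation (assumed). Relative to a final-value comparison, the variance is:

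- final value: 1
- change: 2(1 − ρ)
- baseline-adjusted: 1 − ρ²

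Since 2(1 − ρ) − (1 − ρ²) = (1 − ρ)² > 0, the adjusted variance is the smallest for every ρ strictly between 0 and 1.

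**Power from the formula.** Take the effect that gives the final-value test 80% power at two-sided 5%: (1.960 + 0.842)·√(2/111) = 0.376 SD. Power is then Φ(2.802/√variance − 1.960).

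- ρ = 0.3: change Φ(2.802/√1.4 − 1.960) = 65.8%; adjusted Φ(2.802/√0.91 − 1.960) = 83.6%.
- ρ = 0.5: change 80.0%; adjusted Φ(2.802/√0.75 − 1.960) = 89.9%.
- ρ = 0.7: change 95.1%; adjusted 97.5%.
- ρ = 0.8: change 99.3%; adjusted 99.7%.

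**Simulation on ordered categories.** Assumptions: 111 per arm, bivariate normal latent scores cut into 6 categories, 0.4 SD latent effect, two-sided 5%. The adjusted test is a Wilcoxon test stratified by baseline category (van Elteren) or a rank ANCOVA. Ranges reflect the choice of cut-points and method.

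| Latent ρ | Final value | Change | Baseline-adjusted |
|---|---|---|---|
| 0.3 | 80-82% | 63-67% | 81-83% |
| 0.4 | 80-82% | 69-71% | 85-86% |
| 0.5 | 80-82% | 76-79% | 88-89% |
| 0.6 | 80-82% | 83-86% | 92% |
| 0.7 | 80-82% | 91-93% | 95-96% |
| 0.8 | 80-82% | 97-99% | 99% |

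Type I error stayed near 5% for each test.

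**Gain.** Against the final-value test alone, the gain runs from about 1 point (ρ = 0.3) to 99 − 80 = 19 points (ρ = 0.8). Against the better planned test, it is largest near ρ = 0.5 to 0.6: 89 − 80 = 9 and 92 − 83 = 9 points from the table, and 89.9 − 80.0 = 9.9 from the formula. It falls to about 0 at ρ = 0.8. Allowing for simulation error and other settings, about 0-11 points is a fair range.

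**Sensitivity to the entry rule.** A second simulation let no patient enter with worse than 800 seconds of arc, used 7 categories and a 0.38 SD shift. Latent ρ of 0.3/0.5/0.6/0.7 became observed rank correlations of about 0.22/0.39/0.48/0.58. Power was 79/82/83/85% (final), 67/81/85/93% (change) and 81/88/91/96% (adjusted). The adjusted test was again the best throughout, by 2/6/6/3 points over the better planned test.

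**Two tests without a hierarchy.** With no true effect, at least one of the two planned tests reached two-sided 5% in about 7-10% of simulated trials.

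**The case against.** - **Nothing planned is invalid.** Both Wilcoxon tests hold their error rate under 1:1 randomization, and no stated power target is missed. This stands. A reader might infer that the stereoacuity result would be biased; the documents do not support that.
- **The change test already uses baseline.** The fair comparison is therefore with the better planned test, where the gain is modest. At one-sided 5%, the primary outcome's level, it was only about 0-6 points for correlations of 0.4 to 0.8. This stands, although the better test cannot be identified beforehand.
- **The scale explains the difference from acuity.** A reader might infer that adjustment was left out for no reason, since acuity gets ANCOVA. But stereoacuity is recorded in ordered categories, and an exact rank test is a standard choice that assumes no distribution. This explains why plain ANCOVA was not used; it does not rule out an adjusted rank test.
- **No rule claims success on either test.** A reader might infer that the protocol inflates its error rate to 7-10%. It does not: that figure applies only if either result were taken as proof. Section 1.3 also words the outcome as the 17-week value, which hints that change is supportive. Section 8.7.3 nevertheless gives the two equal standing.
- **The final analysis plan supersedes Chapter 8.** It is not shown and may already differ. As written, the protocol does name the unadjusted test.

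**Conclusion.** The point holds as a modest improvement to one secondary analysis. Section 8.7.3 leaves baseline stereoacuity out of one comparison, subtracts it at a fixed weight in the other, and does not say which comparison counts. A baseline-adjusted rank test was at least as powerful as either planned test at every correlation examined, by about 0-11 points over the better one and about 1-19 over the final-value test alone. The ordering follows from the variance formula. The sizes rest on an assumed correlation, effect, number of categories and cut-points, none of which the protocol gives. A large or certain loss of power cannot be claimed, and neither bias nor an inflated error rate follows from the text.

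**What to change.** In section 8.7.3, or in the final analysis plan if it governs, name one baseline-adjusted comparison of 17-week stereoacuity category as the main stereoacuity analysis. The preferred choice is a Wilcoxon test stratified by baseline category (van Elteren), which can be run as an exact or permutation test and so keeps the exactness the protocol chose. Rank ANCOVA, or a proportional-odds model with baseline category as covariate, would also serve. Report change in categories as a descriptive table.

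The cost is a few lines of wording, with no new data. There are small downsides: sparse baseline categories may need pooling under a rule set in advance, the proportional-odds version adds an assumption to check, and rank ANCOVA gives no directly interpretable effect estimate. The primary analysis and the total of 222 do not change.
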